5. DATA MANAGEMENT

A full data management policy is given in Appendix Q. The four data types will be managed and stored as follows:

1) *Language Explorer Data*

All data will be collected on the Language Explorer app. This will consist of: recordings of the child carrying out the story retell task and the sentence repetition task; the child's responses to the comprehension task; the corrected transcript from the story retell task; and the automatic analysis report from the story retell and sentence repetition tasks. All data collected in the app will be labelled with the child's study ID code and stored on a secure AWS server. The data will be made available to the study team in Bristol who will be able to download the data to the secure servers at North Bristol NHS Trust. Access to the data will be password protected and limited to members of BSLTRU.

A database will be constructed by the study team at BSLTRU which will contain participants' study ID codes and data from each data source. Scores from each of the Language Explorer Assessment tasks will be added when the data are received from Therapy Box.

2) *CELF Assessment Data*

The CELF assessment forms will be labelled with the child's Study ID number, the date of the assessment and the child's date of birth (to facilitate confirmation of the child ID and calculation of standard scores). No identifying information will be included. The forms will be returned along with other study documentation (consent and assent forms) to the study base at BSLTRU in prepaid envelopes given to the recruiting site. Alternatively, they can be scanned on site and emailed to the study team using a secure email address. On receipt at BSLTRU, the forms will be scanned (if hard copy) onto a secure server at North Bristol NHS Trust. The scores from the assessment forms will be added to the study database.

3) Clinical Judgement Forms

These forms will be labelled in the same manner as the CELF assessment forms and sent with them to the study team at BSLTRU. On receipt, the information on the Clinical Judgement forms will be added to the database.

4) Interview data

The recordings and transcripts will be securely stored in the study folder, held on the secure NBT server and labelled with the participants' study ID codes

6. DATA ANALYSIS

Descriptive statistics for the Language Explorer tasks and the CELF assessment scores will be generated.

Initial qualitative analysis of the Language Explorer automatic language analysis report will be carried out to determine scores for outputs obtained in the report (e.g. mean length of utterance, types of words used e.g. nouns, verbs, adjectives and grammatical markers used e.g. regular plural s, possessive s and past tense -ed). Performance on these sub-scores for the clinical sample will be compared with those obtained from children assessed in the separate Citizen Science workstream. Using a known groups methodology, we will determine if the children with DLD can be distinguished from children with typically developing language based on scores on the Language Explorer.

Further analysis will use Language Explorer scores in a correlation analysis with the CELF assessment sub-scores to determine the strength of the relationship between the sub-scores on the Language Explorer and children's performance on the CELF assessment subtests and core scores (also continuous scores).

Cluster analysis of the sub-scores from the Language Explorer app will be carried out to determine if patterns of performance can be observed. Any patterns identified will be

considered against the information on areas of clinical need identified on the Clinical Judgement form and sub-score performance on the CELF.

Transcripts of the SLT and parent/carer interviews will be analysed using thematic analysis, following the process outlined by Braun and Clarke (2006). After reviewing the data, the team will identify initial codes representing themes that arose during the interviews. These initial codes will be discussed through meetings with members of the study team and a common set of initial codes will be agreed upon, named, and defined. Each researcher will apply these codes to their data, all the while remaining open to new codes. Through discussions, these initial codes will be subsequently further refined and re-named as necessary and will then be grouped into sub-themes and cross-checked to ensure that they capture the meanings in the data.

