At the start of the assessment, the SLT will take assent from the study child using the 'Child Assent Form' (Appendix J). If the child is too young or unable to tick the boxes themselves, or the assessment is taking place remotely, the SLT will initial the boxes. If a child is felt not to have provided assent, the assessment session will not go ahead.

Eligibility criteria for children

Inclusion criteria:

- Children aged between 4;0 and 7;11 years
- Children who speak and are exposed to only English in the home
- Children who have been identified by a speech and language therapist as having DLD or suspected DLD. (DLD is defined here as having moderate to severe language difficulties, not associated with other conditions but which is likely to affect their

functioning in school/preschool and likely to persist – based on the clinical judgment of a SLT)

- Case histories that are unremarkable in terms of birth, overall development and general health

Exclusion criteria

- Children with history of significant hearing problems (e.g. sensori-neural hearing loss or use of hearing aids in the case of severe and recurrent otitis media)
- Evidence of structural or neurological disorders (e.g. cleft palate, cerebral palsy, autism)
- Children with significant speech difficulties which impact their intelligibility

Parents/Carers

The 'Consent Form (Parents/Carers)' (Appendix H) seeks consent for the parent to participate in a semi-structured telephone interview carried out by the study team following their child's attendance at the Language Explorer Assessment Clinic. During the interview they will be asked about the experience of their child using the Language Explorer. Consent for this will be an optional element; the parent can consent for their child to participate in the study but choose not to consent to themselves being interviewed. Parents/carers recruited to the study will be assigned a separate but related ID number to that of their child. Processes for maintaining security and confidentiality of the parents/carers identifying information will be the same as that for the child described above.

Parent/Carer eligibility:

- Parent/carer of a child meeting the inclusion criteria for this study

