These are standardised assessments which consist of subtests addressing receptive language, expressive language, language content and language structure. Due to the age range of the children in this study, two different versions of the CELF assessments will be used. The Clinical Evaluation of Language Fundamentals Preschool - Second Edition (CELF- Preschool 2 UK; Appendix K 'CELF-Preschool 2 UK Form') will be used for children aged 4 years 0 months to 5 years and 11 months and the Q-Interactive version of the Clinical Evaluation of Language Fundamentals – Fifth Edition (CELF-5 UK; Appendix L 'CELF-5 UK Form') will be used for children aged 6 years 0 months to 7 years and 11 months. The subtests involve stimuli in the form of pictures and verbal requests which they must respond to, either verbally or through picture selection. For example, within the 'Formulated Sentences' subtest, the child is shown a picture and asked to use a specific word (e.g. 'book') in a sentence about that picture. The child's response is notated verbatim in the score sheet and their responses within and across subtests are scored according to the test manual to provide raw scores which can then be converted to standardised scores (scaled score, percentile rank, age equivalent, confidence interval).

The following subtests are included in each of the two assessments and will need to be completed in the order as follows:

CELF- Preschool 2 UK:

1. Word Structure (Expressive Core)
2. Recalling Sentences (Expressive)

CELF- 5 UK:

1. Word Structure (Expressive Core)
2. Recalling Sentences (Expressive Core)
3. Formulated Sentences (Expressive Core)
4. Understanding Spoken Paragraphs

3) SLT Clinical Judgement Form

A SLT will be asked to complete the 'Clinical Judgement Form' (Appendix M 'Clinical Judgement Form'). This could be the SLT completing the Language Explorer and CELF assessments or another SLT in the team, if they have greater knowledge and experience of the child's skills and areas of need. This form has been designed to gather information about the SLT's clinical judgement of the child based on their observations during the assessment and the child's performance on the subtests and any previous knowledge they have about the child from clinical notes or their own experience.

The data from this will be used to identify whether patterns of performance on the Language Explorer can be matched to observations from the SLTs regarding the child's needs.

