4) SLT and Parent Interviews

An interview schedule will be used to guide qualitative data collection from SLTs and parents/carers, (Appendix O 'Interview Schedule (SLT)' and Appendix P 'Interview Schedule (Parent)').

4.3 PROCEDURES FOR DATA COLLECTION:

The procedures for collecting the data vary for each data type and will be described here:

1) *The Language Explorer*

Each clinical site will collect data from 20 children. Two protocols for collection of Language Explorer data are provided: one for remote facilitation for children aged 6 years 0 months to 7 years 11 months and one for when the app is used in person in the clinical setting for children aged 4 years 0 months to 5 years 11 months.

Remote (ages 6 years 0 months to 7 years 11 months):

Parents will be contacted in advance of the remote appointment by the local SLT and asked to download the Language Explorer app to a compatible device. Wherever possible this will be on a tablet, but if that is not available, the child could be assessed on a mobile phone. At the agreed time for the remote assessment, the SLT will take assent from the child and confirm eligibility and confirm consent as outlined in the consent forms. S/he will then ask the parent facilitating the session to open the Language Explorer app. The SLT will ask the parent to use the child's unique study ID number as their username for the tool. This will ensure that the data can be retrieved by the developers and provided to the local SLT and to the study team at BSLTRU. The parent will then be asked to use the Language Explorer app to collect a language sample from the child using the usual processes involved in the tool (i.e. child hears a story and retells it and then completes comprehension and sentence repetition tasks as described above). The app will record the child's speech as they respond to the stimuli and questions on the tool. For the data to be useful and the child's data to be included in the analysis, the story retell task must be completed as a minimum. The app will use this recording to generate an automated transcription. See Appendix N 'Language Explorer Screen shots' for images taken from the app.

During this, the SLT will observe the process. This is important to facilitate transcription of the recorded sample and for the process of being interviewed by the study team later.

In person in a clinical setting (to include NHS clinics, schools, early years settings) (ages 4 years 0 months to 5 years 11 months):

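### The cluster and CELF correlation analyses make no provision for age, although age band fully determines administration mode and CELF version, so their results may reflect age or mode rather than DLD profiles

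*Protocol*

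**What the plan says.** Section 2.2 admits "Children aged between 4;0 and 7;11 years". Section 4.3 provides two Language Explorer procedures: "one for remote facilitation for children aged 6 years 0 months to 7 years 11 months", and one in person for ages 4;0 to 5;11. In the remote procedure a parent runs the app on a tablet or phone while the therapist watches. In the clinical setting the therapist runs it on a supplied iPad.

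Section 4.2 says that "two different versions of the CELF assessments will be used". CELF-Preschool 2 "will be used for children aged 4 years 0 months to 5 years and 11 months", and CELF-5 "will be used for children aged 6 years 0 months to 7 years and 11 months". Word Structure and Recalling Sentences are in both lists of subtests. Formulated Sentences and Understanding Spoken Paragraphs are in the CELF-5 list only.

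On numbers, section 4.3 says "Each clinical site will collect data from 20 children". There are three sites, so 60 children. The split by age band is not given.

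Section 6 says: "Cluster analysis of the sub-scores from the Language Explorer app will be carried out to determine if patterns of performance can be observed". The outputs it names are mean length of utterance, word classes and grammatical markers. Section 4.2 adds the number correct out of ten comprehension questions and a percentage of words from sentence repetition. Section 6 also plans a correlation of app scores with CELF subtest and core scores. Neither analysis mentions age, band, mode or CELF version. The 600-child normative sample in 6-month age bands (section 4.1) is used only to compare children with DLD against typically developing children.

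**The concern.** Mean length of utterance, grammatical markers and items correct can be expected to rise between ages 4 and 8. Clustering looks for the largest common source of variation. If that source is age, or the difference between a therapist in clinic and a parent at home, two clusters can form that are simply the two age bands.

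The planned cross-check is weak protection. Section 6 compares clusters with CELF sub-scores, but CELF content also differs by band, so a cluster that is really the older, remote group would come with its own CELF profile.

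Section 4.1 says these patterns could later guide clinical need and management, and that the data will inform whether a fully powered study is required. An age or mode split reported as a DLD pattern would mislead both.

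**Working it through.** The protocol gives no sample-size, power or precision figure for these analyses, so there is nothing to reproduce. The only count is 3 × 20 = 60 children.

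**How far age and mode overlap.** Take age as uniform over 4 to 8 years, with a cut at 6. Variance of age = 4²/12 = 1.333. Band means are 5 and 7, so between-band variance = 1. R² = 1/1.333 = 0.75, correlation = √0.75 = 0.87, variance inflation = 1/(1 − 0.75) = 4.0. No age is tested in both modes, so the two effects can be separated only by assuming the shape of the age trend.

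**Clustering.** Simulation: 60 children (30 per band, assumed), 8 standardised sub-scores, shared severity variance 0.3, residual variance 0.7, two true profiles (half the sub-scores raised, half lowered), k-means with k = 2, 200 datasets per cell. Assumed, because the documents give none of them: age slope, mode shift and profile contrast. Entries are the mean adjusted Rand index with age band / with true profile (0 = chance, 1 = perfect).

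| Slope (SD/year) | 1.0 SD profiles, no mode shift | 1.0 SD, mode shift 0.5 SD | 1.5 SD, no mode shift | 1.5 SD, mode shift 0.5 SD |
|---|---|---|---|---|
| 0 | 0.00 / 0.41 | 0.07 / 0.25 | 0.00 / 0.97 | 0.00 / 0.97 |
| 0.15 | 0.03 / 0.35 | 0.21 / 0.06 | 0.00 / 0.97 | 0.01 / 0.94 |
| 0.3 | 0.12 / 0.13 | 0.35 / 0.01 | 0.00 / 0.96 | 0.11 / 0.68 |
| 0.5 | 0.29 / 0.01 | 0.53 / 0.01 | 0.08 / 0.71 | 0.48 / 0.08 |
| 0.75 | 0.45 / 0.00 | 0.64 / 0.00 | 0.40 / 0.09 | 0.63 / 0.01 |

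The same setting (slope 0, 1.0 SD, no shift) run twice gave 0.41 and 0.49 for profile, so small differences should not be read closely; 0.12 against 0.13 is a tie. For two equal groups the index is roughly (2p − 1)², where p is the share of children matched: 0.29 means p ≈ (1 + √0.29)/2 = 0.77.

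With no true profiles and no mode shift, the index with band is still 0.12, 0.28 and 0.45 at 0.3, 0.5 and 0.75 SD/year.

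**After correction** (1.0 SD profiles, slope 0.5, mode shift 0.5): unadjusted 0.53 / 0.01; age-standardised 0.07 / 0.30; age and mode both removed −0.01 / 0.43. The age-standardised run removes the true slope exactly, which is a best case.

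**Correlation.** Let b be the app's age slope and v = b² × 16/12. At b = 0.5, v = 0.333.

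- Raw app score with age-scaled CELF: r/√(1 + v). For r = 0.50: 0.50/1.155 = 0.43. For r = 0.60: 0.52. A true 0 stays 0.
- Raw app score with raw CELF of the same slope: (r + v)/(1 + v). For r = 0.50: 0.833/1.333 = 0.63. A true 0 becomes 0.25. This treats the two CELF versions as sharing a raw scale, which they do not.
- Within one version the age range is 2 years: v = 0.25 × 4/12 = 0.083, and 0.50 becomes 0.50/1.041 = 0.48.

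**Precision when split** (Fisher z, r = 0.6, z = 0.693): n = 60, 0.693 ± 1.96/√57 gives 0.41 to 0.74; n = 30, 0.693 ± 1.96/√27 gives 0.31 to 0.79.

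**The case against.** A reader might infer that the analyses will mainly recover age and mode. The documents do not support that. They give no growth rate, mode effect or profile strength, and the result reverses with strong profiles: 0.71 for profile against 0.08 for band at 0.5 SD/year without a mode shift. The correct word is may.

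Nor does section 6 say outright that bands are pooled or that scores enter raw. Section 1.2 counts a scaled score among the things existing technology lacks, and an analysis plan not shown could add age adjustment. This stands as a caution. However, section 6 describes each analysis once, without a split, on outputs that are raw quantities, and gives the norms another purpose. The tie between age, mode and CELF version is fixed by the design, whatever an analysis plan adds.

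For the correlations, a reader might infer false associations. With scaled CELF scores, which section 4.3 has the therapists derive, there is only modest dilution. Inflation requires raw CELF scores, which section 6 does not specify. For the two subtests found only in CELF-5, the correlation is already within one version.

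Clusters are also compared with the Clinical Judgement Form. That is a partial safeguard, but section 4.2 lets performance on the subtests inform the form.

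Finally, section 4.1 calls the data exploratory. That lowers the severity; it does not make an age split interpretable as a DLD pattern.

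**Conclusion.** The concern holds as a risk. Age band, mode, operator and CELF version coincide completely, and section 6 provides nothing to keep them out of the clusters or the correlations. With profile contrasts of 1.0 SD and no mode effect, band matches or beats profile from about 0.3 SD/year of growth; with a 0.5 SD mode shift, band already leads at 0.15 SD/year. With 1.5 SD contrasts and no mode effect, the profiles survive at 0.5 SD/year and lose at 0.75. The correlation problem is smaller: 0.50 to about 0.43 at 0.5 SD/year with scaled CELF scores, and inflation on scales that are not comparable if raw scores are used.

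All these sizes rest on assumed slopes, shifts and contrasts and on an even split of bands. Given the exploratory status, this is a should-fix. The absence of a recruitment quota by band is not an error.

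**What to change.** In section 6:

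1. Cluster on sub-scores age-standardised against the normative sample. The app already records birth month and year (section 9.3). Confirm that the norms cover 4;0 to 7;11, since section 4.1 does not state their range.
2. Section 1.3 describes parents and carers running the app for the norms, so standardising leaves any mode difference in the therapist-run band. Also centre within band, or repeat the clustering within each band.
3. Tabulate cluster membership against band.
4. Correlate age-standardised app scores with CELF scaled scores within each CELF version. Combine the two estimates only for Word Structure and Recalling Sentences.
5. State that age and mode effects cannot be separated in this design.

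A quota by band and continuous modelling of age are optional.

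The cost is a few lines of text, with no extra children or measurements. Centring removes any real difference between bands, although the design cannot attribute such a difference anyway. Within-version correlations are less precise: for r = 0.6, a 95% interval of 0.31 to 0.79 at n = 30 against 0.41 to 0.74 at n = 60, partly recovered where two estimates are combined.

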2. PARTICIPANT ENTRY

2.1 SETTINGS

The evaluation will take place across three clinical sites: Sirona Care and Health (Bristol), City & Hackney NHS Trust and Newcastle Upon Tyne NHS Foundation Trust. The speech and language therapy service delivery model for the three clinical sites varies: Bristol and Hackney have similar care pathways while Newcastle's is different. Some study procedures will therefore vary for Newcastle; details of how will be explained throughout the protocol.

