3. OBJECTIVES

- (1) Determine whether Language Explorer can distinguish children with DLD from those who have typically developing language

- (2) Determine whether patterns of performance on Language Explorer can be observed for different groups of children with DLD
- (3) Understand clinician and parent/carer views of Language Explorer

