The SLT carrying out the assessment sessions will follow exactly the coronavirus infection control protocols for carrying out assessments in person in a clinical setting, as specified by their service. At the start of the assessment, the SLT will take assent and confirm eligibility and consent as described above. The SLT will then open the Language Explorer app and use the child's unique study ID number as their username and use the app to collect a language sample, as described for the remote setting. The SLT service will have been provided with iPads with Language Explorer already loaded. Once data collection for the Language Explorer app is complete, the SLT will begin the assessment on the Clinical Evaluation of Language Fundamentals assessment as described below.

2) *The CELF Assessments and Clinical Judgement Form*

Remote (ages 6 years 0 months to 7 years 11 months):

When the child has completed all tasks of the Language Explorer app, assessed using the Q-Interactive version of the CELF-5, completing these tasks in order: Word Structure (Expressive Core), Recalling Sentences (Expressive Core), Formulated Sentences (Expressive Core), Understanding Spoken Paragraphs. The child's direct involvement in data collection ceases at this point and the appointment can be concluded.

In person (ages 4 years 0 months to 5 years 11 months):

When the child has completed all tasks of the Language Explorer app, the child will be assessed by the SLT using the CELF-Pre-school 2 assessment. The subtests of the CELF assessments will be carried out in the order: Word Structure (Expressive Core) followed by Recalling Sentences (Expressive).

The SLT will be able to carry out any additional assessments that s/he would typically use to inform clinical judgement of the child's language competence but data from these will not be collected by the study team or used in the research.

Following completion of the CELF assessments carried out by the SLT, the SLT will score the CELF assessment for raw scores, sum of subtest scaled scores, standard scores, percentile ranks and confidence intervals, following the scoring guidelines in the manuals. Once the scoring has been carried out, the SLT will complete the Clinical Judgement form. Alternatively, the SLT who has completed the Language Explorer and CELF assessments can ask another SLT in the team who is more familiar with the child to complete the Clinical Judgement Form.

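### Agreement between app clusters and the CELF cannot show that distinct DLD patterns exist, because bands of severity would agree with the CELF too

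*Protocol*

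**What the plan says.** Aim 2 (Protocol section 3) is to "Determine whether patterns of performance on Language Explorer can be observed for different groups of children with DLD". Section 6 gives that question to one analysis: "Cluster analysis of the sub-scores from the Language Explorer app will be carried out to determine if patterns of performance can be observed". Any patterns found are then to be "considered against the information on areas of clinical need identified on the Clinical Judgement form and sub-score performance on the CELF".

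Section 6 states no comparison with a one-group solution, no step separating the shape of a child's profile from overall level, and no adjustment of the clustered sub-scores for age. It also plans to use app scores "in a correlation analysis with the CELF assessment sub-scores", so the two instruments are studied as related measures.

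Section 2.2 sets the severity range: "DLD is defined here as having moderate to severe language difficulties". At ages 4;0 to 5;11 the CELF consists of two expressive subtests only (sections 4.2 and 4.3). The Clinical Judgement Form is completed once the CELF has been scored (section 4.3) and may draw on subtest performance (section 4.2). Section 4.1 calls the data exploratory, but says such patterns could later guide services on clinical need and management.

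**The concern.** Obtaining clusters is weak evidence of patterns, since k-means or hierarchical clustering cut at two or more groups yields groups from any data. The weight therefore falls on the comparison with the CELF and the form. If the sub-scores simply rise and fall together with overall language level, clustering separates lower from higher scorers, and those groups will differ on any other language measure. A continuum then looks like confirmed subgroups.

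The second source does little to break the circle, because whoever completes the form may already know the CELF result. In the younger children, two expressive subtests cannot show a receptive-versus-expressive contrast. If sub-scores such as mean length of utterance enter unadjusted over a four-year age span, the clusters may partly be age bands.

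At stake is a report of DLD patterns, offered as a basis for later guidance, where the data show only more and less severe difficulty.

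**Working it through.** The protocol gives no figure to reproduce, so the question is how often the planned comparison would look positive if there were no subgroups.

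**Inputs from the protocol.** "Each clinical site will collect data from 20 children" (section 4.3) and "The evaluation will take place across three clinical sites" (section 2.1), so 3 × 20 = 60 children. The total is not stated as such.

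**Assumed inputs** (the protocol gives none): 9 sub-scores; one severity factor with loading λ of 0.5 to 0.7; CELF correlation r with that factor of 0.4 to 0.6; a two-sided 5% test of the CELF between two clusters.

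**Hand check.** Treat the two clusters as a split at the median of the mean sub-score, 30 against 30.
1. Reliability of the mean score as a measure of the factor: 9λ² / (1 + 8λ²). At λ = 0.6 this is 3.24 / 3.88 = 0.835, with square root 0.914.
2. Correlation of mean score with CELF at r = 0.5: 0.5 × 0.914 = 0.457.
3. A median split multiplies this by √(2/π) = 0.798, giving 0.365.
4. Standardised CELF difference: 2 × 0.365 / √(1 − 0.365²) = 0.78.
5. Non-centrality: 0.78 × √15 = 3.03. The chance of p < 0.05 is about Φ(3.03 − 2.00) = 0.85.

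The same steps give 0.59 at λ = 0.5, r = 0.4 and 0.97 at λ = 0.7, r = 0.6.

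**Simulation with actual clustering, no subgroups, 60 children.**
- Two-cluster k-means over these ranges: the CELF differed in 56 to 98% of runs. Other runs over the same ranges, some with three clusters, gave 50 to 99%. Clustering on profile shape instead (each child's own mean subtracted) gave 1 to 6%.
- A wider set used 6 or 10 sub-scores, inter-correlations of 0.3 to 0.7, k-means or Ward, and 2 to 5 clusters chosen by silhouette:

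| CELF correlation with factor | CELF differs between clusters | After overall level is removed |
|---|---|---|
| 0.4 | 48 to 74% | 0 to 1% |
| 0.6 | 85 to 99% | 0 to 1% |
| 0.8 | 99 to 100% | 0 to 1% |

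Cluster membership explained 56 to 66% of the variance in overall app level, close to the 2/π = 64% of a plain median split. With mutually unrelated sub-scores and an unrelated CELF, groups were still returned every time but the CELF differed in only 8% of runs. Shared level is what produces the agreement.

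**Allowing one group.** On subgroup-free data (8 sub-scores, inter-correlation 0.5), a gap statistic kept one group in 92% of runs with a uniform reference and 100% with a single multivariate-normal reference.

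**Power of the remedy.** Two true, equal groups with opposite profiles, tested on profile shape against a single-population reference, were detected in 0 to 1% of runs at differences of 0.75 to 0.8 SD per sub-score, 8 to 29% at 1.0 SD and 78 to 88% at 1.25 SD, depending on the simulation set-up. Without removing level, one set-up gave 0% at 1.0 SD and 14% at 1.2 SD.

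Age was not simulated. The age-band point is reasoning from the stated age range.

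**The case against.** A reader might infer that the analysis can never answer no. The text does not support that. Section 6 names no algorithm, some clustering methods (model-based selection, the gap statistic) can return one group, and the wording is conditional throughout. The algorithm and the rule for the number of clusters may properly sit in an SAP that is not shown.

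A reader might also infer that any clusters found would be nothing but severity bands. That does not follow either. Real profiles may exist; the planned comparison cannot tell the two apart.

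Nor are the percentages an error rate of this study. The protocol states no test, no significance level and no rule for confirmation, the one-factor model is an assumption, and the simulation reduces the CELF to one score and omits the form. A careful reading of several sub-scores and areas of need might reveal a low-everywhere group for what it is.

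Finally, the study is labelled exploratory and its clinical use is conditional and deferred.

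These points limit the claim and its consequence. They do not remove it: choosing an algorithm leaves agreement with the CELF just as uninformative about profiles, and section 6 contains no step that separates level from shape.

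**Conclusion.** The concern holds in a limited form. As written, clusters followed by agreement with the CELF or the form cannot distinguish DLD profiles from one severity continuum, and unadjusted sub-scores leave age bands open as well. With no subgroups and about 60 children, apparent agreement with the CELF would arise in roughly 50 to 99% of cases under the assumed loadings of 0.5 to 0.7 and CELF correlations of 0.4 to 0.6. The exact figure depends on those assumptions; the direction was the same in every setting with a shared factor. The change is worth making because it is cheap and bears directly on aim 2. The exploratory label keeps it from being critical.

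**What to change.** In section 6, keep the cluster analysis and add the following.
- Cluster age-standardised sub-scores. The normative sample in six-month bands (section 4.1) is a natural source.
- Allow a one-group solution.
- Compare the chosen solution with a single-population reference having the same covariance, for example by parametric bootstrap.
- Report whether clusters differ in profile shape after overall level is removed, before treating agreement with the CELF or the Clinical Judgement Form as evidence of patterns.
- Report stability under resampling descriptively, without a fixed cut-off.
- State the wording of the conclusion in advance. A negative result reads *distinct patterns not shown*; it does not establish that variation lies along overall severity. A positive result is labelled exploratory.

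The cost is a few sentences of protocol and a small amount of code, with no extra children or visits. The real price is low power at about 60 children for profile differences of about 1 SD or less per sub-score, so genuine moderate patterns may go undetected.
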